8.3 Analysis of Secondary Outcome Measures

8.3.1 PFS according to RECIST v1.1 in participants with Detectable Programmed Death-Ligand 1 (PD-L1)

PFS according to RECIST v1.1 in participants with Detectable Programmed Death-Ligand 1 (PD-L1) will be calculated using Kaplan-Meier curves, and the median PFS will be read from this curve. Note: The PD-L1 expression testing will be performed at baseline. Breast tissue (primary or metastatic site) collected to analyze for the presence of CCR5 at pre-screening will additionally be used for evaluating PD-L1 expression levels.

8.3.2 Overall response rate (ORR) and clinical benefit rate (CBR) in subjects with CCR5+ mTNBC treated with leronlimab (PRO 140) and carboplatin

Overall response rate (ORR) and clinical benefit rate (CBR) in subjects with CCR5+ mTNBC treated with leronlimab (PRO 140) and carboplatin will be calculated using proportions and 95% confidence intervals.

Note: Overall response rate defined as the proportion of patients who achieve an overall response of complete response or partial response in the total number of evaluable patients, assessed by RECIST v1.1. Clinical benefit rate is defined as the proportion of patients who achieve an overall response of complete response or partial response or stable disease in the total number of evaluable patients, assessed by RECIST v1.1. Imaging scans to be done at the end of 2 cycles (i.e., every 6 weeks) for the first 6 cycles (18 weeks) and at the end of 3 cycles (i.e., every 9 weeks) thereafter.

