Note: Overall response rate defined as the proportion of patients who achieve an overall response of complete response or partial response in the total number of evaluable patients, assessed by RECIST v1.1. Clinical benefit rate is defined as the proportion of patients who achieve an overall response of complete response or partial response or stable disease in the total number of evaluable patients, assessed by RECIST v1.1. Imaging scans to be done at the end of 2 cycles (i.e., every 6 weeks) for the first 6 cycles (18 weeks) and at the end of 3 cycles (i.e., every 9 weeks) thereafter.

- Time to new metastases (TTNM);

Note: Recorded time from baseline metastatic disease (at time of enrollment) to the time of development of new metastasis in different site. New metastases in same site will be also recorded.

- The change from baseline in circulating tumor cells (CTC) level in the peripheral blood.

Note: Reported unit of measure will be the number of CTCs/milliliter. CTCs enumeration will be performed at baseline and at the time of response assessment. Fraction of baseline positive and change from ≥ 5 CTCs will be recorded and reported.

- Overall survival defined as time in months from the date of first study treatment to the date of death;

Note: Patients will be followed from the start of treatment until 2 years post-treatment or death, whichever occurs first, and average survival time will be measured.

- The number, frequency, and severity of AEs collected from the time of first treatment until 12 weeks after study treatment completion to evaluate safety of leronlimab (PRO 140) and Carboplatin in subjects with CCR5+ mTNBC.

Exploratory Outcome (Endpoints) Measures:

- Measure immune biomarkers (PD-L1) in CTCs, metastatic tissue and immune cells such as CAMLs and correlate with therapeutic benefit (PFS); and

- Correlation between CCR5 expression (CTCs, CAMLs) and PD- L1 expression.

PFS will be calculated using Kaplan-Meier curves and the median PFS will be read from this curve. Response rates (overall response rate, clinical benefit rate) will be calculated using proportions and 95% confidence intervals. Time to new metastases and overall survival will also be analyzed using Kaplan-Meier curves. Exploratory serial blood markers will be related to PFS using Cox regression, and to response using logistic regression.

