6. ANALYSIS POPULATIONS

6.1.1 Intent-to-Treat (ITT) Population

The ITT population is defined as the set of subjects who have received at least one dose of leronlimab (PRO 140) and have measurable disease at baseline. The ITT population will be used as the primary analysis population.

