6.1.2 Per Protocol (PP) population

The Per Protocol (PP) population is defined as the set of subjects who meet the ITT population requirements, were not associated with any major protocol violations and have received at least 2 cycles of treatment. This population will be identified before the database lock. The PP analysis of primary and secondary outcome measures will be considered supportive.

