7.3 Handling of Missing Data

All data will be used as observed, and no imputations will be made for any missing data point. All summaries will be based on observed data only.

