7.4 Sensitivity Analysis

There will be no sensitivity analysis for this Phase Ib/II study.

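### ORR and CBR are divided by an undefined set of evaluable patients, not reconciled with the primary ITT population, so treated patients without a usable scan can leave the denominator and raise both rates

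*SAP*

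**What the plan says.** SAP 8.3.2 takes both rates as proportions "in the total number of evaluable patients", with 95% confidence intervals of unnamed type. SAP 2.4.2 has the same definition. So does the protocol, in the synopsis and in section 8.7.3.1, where ORR is the proportion with "complete response or partial response in the total number of evaluable patients". The wording therefore did not originate in the SAP.

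On populations, SAP 6.1.1 defines ITT as "subjects who have received at least one dose of leronlimab (PRO 140) and have measurable disease at baseline" and adds: "The ITT population will be used as the primary analysis population". No post-baseline scan is required. SAP 6.1.2 says "The PP analysis of primary and secondary outcome measures will be considered supportive", which implies that ITT is the main set for ORR and CBR as well as for PFS. SAP section 6 defines ITT, per-protocol and safety populations, and no response-evaluable one.

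On missing data, SAP 7.3 says "All data will be used as observed, and no imputations will be made for any missing data point" and "All summaries will be based on observed data only". SAP 7.4 says "There will be no sensitivity analysis for this Phase Ib/II study". The time-point response table in protocol 7.15.6 has an inevaluable (NE) category, but neither document says whether a patient who is only ever NE, or who is never scanned after baseline, counts in the response denominator.

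**The concern.** The plan names one population as primary and then defines two secondary endpoints over another, without saying who belongs to it. The patients affected are those treated but without a usable post-baseline assessment: death, clinical decline or withdrawal before the first scan at week 6, or NE only. If they are left out, the numerator stays the same and the denominator shrinks, so the rate can only go up.

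This matters more in a single-arm trial. No control arm carries the same bias, and the response rate will be read against outside experience. The study is also open-label, so an undefined denominator could be settled after the responses are known.

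**Working it through.** **1. Is there a planned figure to reproduce?** No. The plan gives no ORR or CBR target, and SAP section 3 bases the 30 Phase II patients on clinical judgment without a power calculation. The numbers below are illustrations.

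**2. What does *evaluable* mean here?** Three places bear on it.
- SAP 8.2.2 (PFS) uses the word for tumour assessments. It provides a censoring rule for a patient who has no evaluable assessment, and it lists incomplete, unperformed and missing assessments together as having no data. Evaluability there describes the scan data, and the plan expects some patients to have none. They get a rule for PFS and none for response.
- Protocol 7.15.6 uses NE for a time point whose response cannot be determined, which is again a property of the scan.
- Protocol 7.10 treats anyone with at least one dose as evaluable, but only for toxicity.

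For tumour endpoints the natural reading is that a patient with no usable post-baseline assessment is not evaluable. SAP 7.3 points the same way, and SAP 7.4 removes any check on it.

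**3. Size of the effect.** Let N = 30 (SAP section 3, taking all 30 as meeting the ITT definition), x = patients with the event (assumed), and k = ITT patients left out as not evaluable (assumed).

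ITT rate = x/30. Evaluable rate = x/(30−k). Ratio = 30/(30−k).

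Intervals are exact (Clopper-Pearson) 95%.

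| k | Denominator | Ratio | ORR, x = 9 | CBR, x = 20 |
|---|---|---|---|---|
| 0 | 30 | 1.00 | 30.0% (14.7–49.4) | 66.7% (47.2–82.7) |
| 2 | 28 | 1.07 | 32.1% (15.9–52.4) | 71.4% (51.3–86.8) |
| 3 | 27 | 1.11 | 33.3% (16.5–54.0) | 74.1% (53.7–88.9) |
| 4 | 26 | 1.15 | 34.6% (17.2–55.7) | 76.9% (56.4–91.0) |

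**4. What is a plausible k?** The documents give none. As a rough guide, protocol 1.5 quotes a median survival of 9–12 months after recurrence. Assume exponential survival and take the first scan at week 6, which is 42/30.4375 = 1.38 months.

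P(death before scan) = 1 − 2^(−1.38/m).
- m = 9 months: 10.1%, or 30 × 0.101 = 3.0 patients. P(at least one) = 1 − (1 − 0.101)^30 = 96%.
- m = 12 months: 7.7%, or 30 × 0.077 = 2.3 patients. P(at least one) = 91%.

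This probably overstates early deaths, because entry requires ECOG 0–1 and a life expectancy of at least 6 months. Withdrawals and NE-only patients would add to it. Two to three is a reasonable guide, and k = 4 lies above it.

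**The case against.** A reader might infer that the plan drops early failures and so inflates both rates as a matter of course. The documents do not support that. No sentence says who is excluded, and several provisions keep early failures in:
- A patient with RECIST progression on the first scan has an assessment and counts as a non-responder.
- Protocol 7.15 continues tumour assessments when dosing is interrupted and specifies a scan at end of treatment (although the visit list in 4.4.1 omits imaging).
- Under protocol 4.4, patients who stop for toxicity without progression are imaged every 9 weeks until progression.

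It can also be argued that *evaluable* simply means ITT. ITT already requires measurable disease at baseline, and protocol 8.7.3.1 assigns the primary analysis to ITT under the heading that also lists ORR and CBR. On that reading there is no inflation. It remains possible, but it fits poorly with how SAP 8.2.2 and protocol 7.15.6 use the term. The no-imputation rule is indirect support only, since it does not itself set a denominator.

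Two further points stand. Counting an unscanned patient as a non-responder is a convention: someone who withdraws before week 6 has unknown response and, for CBR, might have been stable. And the shift is small beside the sampling error. At k = 4 the ORR moves 4.6 points, while the exact interval for 9/30 is about 35 points wide. SAP section 5 plans no formal test, and the by-subject efficacy listings in SAP 12.1 could let an ITT rate be recovered later.

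**Conclusion.** The concern holds in conditional form. The denominator is undefined for response and unreconciled with ITT. On the more natural reading it leaves out treated patients with no usable post-baseline assessment, and that can bias ORR and CBR only upward.

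At k = 2–3 the gain is 2.1–3.3 points on an assumed 30.0% ORR and 4.8–7.4 points on an assumed 66.7% CBR. At k = 4 it is 4.6 and 10.3 points. At k = 0, or if *evaluable* is taken as ITT, it is nil. These figures rest on assumed event counts, an assumed k, and all 30 patients meeting the ITT definition.

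No error rate or decision rule is affected, because both endpoints are secondary and descriptive. The point is still worth acting on: the direction is known, there is no control arm, and no planned analysis would show the size of the bias.

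**What to change.** Change SAP 2.4.2 and 8.3.2, and the matching protocol text in the synopsis and section 8.7.3.1, so that:
- the denominator for ORR and CBR is the ITT population;
- a patient whose response is NE throughout or missing counts as a non-responder for ORR and as without clinical benefit for CBR, stated as an explicit exception to SAP 7.3;
- the 95% intervals are named as exact (Clopper-Pearson);
- any response-evaluable rate has an explicit definition and is supportive only, with the number of patients left out and the reasons shown beside it.

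A change to the SAP alone would leave it contradicting the protocol's endpoint definition, so the protocol needs an amendment or the departure must be documented. No new data are needed. The cost is wording in two documents and slightly less favourable reported rates.

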8.3.3 Time to new metastases (TTNM)

Time to new metastases (TTNM) will be calculated using the formula in Section 7.9.3 and summarized descriptively. Kaplan-Meier analysis will be used to depict the median time (days) to new metastases.

Note: Recorded time from baseline metastatic disease (at time of enrollment) to the time of development of new metastasis in different site. New metastases in same site will be also recorded.

8.3.4 The change from baseline in circulating tumor cells (CTC) level in the peripheral blood The change from baseline in circulating tumor cells (CTC) level in the peripheral blood will be

calculated for each subject at each timepoint and summarized descriptively.

Note: Reported unit of measure will be the number of CTCs/milliliter. CTCs enumeration will be performed at baseline and at the time of response assessment. Fraction of baseline positive and change from ≥ 5 CTCs will be recorded and reported.

8.3.5 Overall survival defined as time in months from the date of first study treatment to the date of death

Overall survival defined as time in months from the date of first study treatment to the date of death will be presented using proportions and 95% confidence intervals.

Note: Patients will be followed from the start of treatment until 2 years post-treatment or death, whichever occurs first, and average survival time will be measured.

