2. PROTOCOL DESIGN

2.1 Design Overview

Phase Ib

Phase Ib is a dose escalation phase with 3 dose levels (cohorts) of leronlimab (PRO 140) administered in combination with a fixed dose of carboplatin at AUC 5. This dose finding portion of study will follow a "3+3" designed to determine the maximum tolerated dose (MTD) of leronlimab (PRO 140) administered as subcutaneous injection in subjects with histologically confirmed mTNBC that express CCR5. The MTD is defined as 1 dose level (cohort) below the dose in which dose limiting toxicities (DLTs) were observed in ≥ 33% of the participants.

A schematic of the "3 + 3" Dose Escalation Study Design is provided in Appendix 2.

Cohorts of 3 patients are entered at given dose level K. If no patients have a DLT, then the dose will be escalated to the next dose level, K+1. If more than 1 subject has a DLT then the previous dose level, K-1, will be considered as MTD. If 1 subject has a DLT an additional 3 patients will be treated at this dose level, K. If no further subjects suffer a DLT then the dose level will be escalated to K+1 and if any further subjects have a DLT then the previous dose level, K-1, will be considered the MTD. The MTD will be the maximum dose level with an observed toxicity rate of 0% or 17%. If any of the SAEs or DLTs outlined above have occurred, the Data Safety Monitoring Board (DSMB) will conduct an independent review of the data and make a final decision for dose escalation to the next cohort.

The final decision on the MTD will be made following a review of the study data by the DSMB. Continuation into Phase II of the study will take place after the DSMB meeting.

Once the MTD has been determined, subjects enrolled in lower dose cohorts will be allowed to escalate the dose to the MTD, if acceptable per the Investigator's discretion.

Phase II

Phase II is a single arm study with 30 patients in order to test the hypothesis that the combination of carboplatin AUC 5 intravenously and MTD of leronlimab (PRO 140) SC will increase PFS in patients with CCR5 + mTNBC. PFS in patients with newly recurred TNBC is approximately 5 months.

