7.9.3 Time to event

Time to event will be calculated according to the formula noted below:

Time to event = (Date of Event
$$-$$
 Date of first treatment) + 1

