8. STATISTICAL METHODS

All data from this clinical trial will be provided in data listings, study drug, clinical trial center, subject, and time point (if applicable).

Data summary will be according to the variable type:

- Continuous data summaries will include:
 - Number of observations, mean, standard deviation, median, and minimum and maximum values.

- Categorical data summaries will include:
 - o Frequency counts and percentages.

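### SAP 8.3.3 adds to its valid Kaplan-Meier median for time to new metastases a descriptive summary that covers only patients with an event and is therefore biased short

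*SAP*

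**What the plan says.** SAP 8.3.3 has two analysis sentences. The first is "Time to new metastases (TTNM) will be calculated using the formula in Section 7.9.3 and summarized descriptively". The second is "Kaplan-Meier analysis will be used to depict the median time (days) to new metastases". A note then defines the event: "Recorded time from baseline metastatic disease (at time of enrollment) to the time of development of new metastasis in different site". Death is not named as an event.

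Three general sections govern the first sentence:

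- SAP 7.9.3: "Time to event will be calculated according to the formula noted below". The formula is date of event minus date of first treatment, plus 1. It has no term for a censoring date.
- SAP 8, on continuous data: "Number of observations, mean, standard deviation, median, and minimum and maximum values".
- SAP 7.3: "All summaries will be based on observed data only".

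Protocol 8.7.3.1 plans only the Kaplan-Meier analysis: "Time to new metastases and overall survival will also be analyzed using Kaplan-Meier curves". The protocol synopsis agrees. SAP 8.2.2 gives detailed censoring rules for progression-free survival (PFS); SAP 8.3.3 gives none for TTNM.

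**The concern.** A patient who never develops a new metastasis has no event date, so the 7.9.3 formula returns no value for her. A programmer who follows 8.3.3, 7.9.3, 8 and 7.3 literally would produce a table of TTNM in which event-free patients are simply absent. Those are the patients with the longest times relative to their follow-up, so the mean and plain median are pulled down. The result would sit beside a Kaplan-Meier median that keeps the same patients in the risk set, and the SAP does not say which figure prevails.

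The wording looks deliberate enough to be acted on. PFS in SAP 8.2.2 and PFS in PD-L1-detectable patients in 8.3.1 are assigned Kaplan-Meier without any descriptive summary. The change in circulating tumor cells in 8.3.4 carries the same descriptive instruction as TTNM, and there it does mean an ordinary continuous summary.

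At stake is how one named secondary objective is reported. SAP 5 plans no formal hypothesis test, so the descriptive and Kaplan-Meier figures are themselves the TTNM result.

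**Working it through.** **Inputs from the documents.** Phase II size: "Phase II is a single arm study with 30 patients". The only time-to-event benchmark is a PFS of about 5 months (SAP 2.1), which is not a TTNM figure. The documents give no expected TTNM and no expected event share, so there is no plan figure to reproduce.

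**Assumptions, not in the documents.** TTNM is exponential with hazard a. Censoring is independent of it, either exponential with hazard c or at one fixed time. Event shares of 30% to 90% are examined.

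**Step 1, closed form with exponential censoring.** The share of patients with an event is p = a/(a + c). Among patients with an event, the observed time is exponential with rate a + c. Hence:

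- events-only mean = 1/(a + c) = p × (1/a) = p × true mean
- events-only median = ln 2/(a + c) = p × true median

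For a true median of 5 months the true mean is 5/ln 2 = 7.21 months. At p = 0.5 the events-only mean is 0.5 × 7.21 = 3.61 and the median 0.5 × 5 = 2.50. At p = 0.9 they are 6.49 and 4.50; at p = 0.3, 2.16 and 1.50.

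**Step 2, simulation with 30 patients** (4000 runs per setting, true median 5 months, true mean 7.21). Events-only results in months, with the percentage of the true value:

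| Event share | Mean, exponential censoring | Median, exponential censoring | Mean, fixed-time censoring | Median, fixed-time censoring |
|---|---|---|---|---|
| 90% | 6.48 (90%) | 4.60 (92%) | 5.35 (74%) | 4.38 (88%) |
| 70% | 5.05 (70%) | 3.62 (72%) | 3.50 (48%) | 3.17 (63%) |
| 50% | 3.63 (50%) | 2.64 (53%) | 2.22 (31%) | 2.10 (42%) |
| 30% | 2.18 (30%) | 1.66 (33%) | 1.21 (17%) | 1.18 (24%) |

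The exponential columns agree with step 1 apart from small-sample error in the median. A true median of 8 months gives almost the same percentages. The shortfall runs from 100% − 92% = 8% to 100% − 17% = 83%.

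**Step 3, the Kaplan-Meier median in the same simulations.** With exponential censoring it is 4.92, 4.99 and 5.03 months at 90%, 70% and 50% events. At 30% it is 4.59 when reached, and it is not reached in 18% of runs. With fixed-time censoring it is 4.75 and 4.77 at 90% and 70%, not reached in 42% of runs at 50%, and not reached in 98% at 30%. When events are few, Kaplan-Meier usually shows it by leaving the median unreached. The events-only median gives a number regardless.

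**Step 4, what the events-only figure measures.** A new lesion counts as progression (Protocol 7.15.4). Suppose observation for new metastases stopped at progression or death, with an exponential median of 5 months. The combined rate a + c is then ln 2/5, so the events-only median is 5 months whatever the true TTNM. For true medians of 7.5, 10 and 15 months that is 67%, 50% and 33% of the truth. Under this assumption the figure repeats PFS and says little about TTNM.

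**The case against.** The strongest reply is that the second sentence of 8.3.3 can be read as explaining how the first is to be carried out. The SAP uses its summary wording loosely: the maximum tolerated dose is also to be described in that way (8.2.1), and in 8.4.2.1 the time to onset of an injection-site reaction is summarized by Kaplan-Meier. No separate TTNM table is listed; SAP 12.2 names only efficacy summaries in general. SAP 7.3 is a missing-data rule, and an event-free patient is censored, not missing.

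Part of this stands. A reader might infer from the first sentence that the SAP's median for TTNM drops every event-free patient. The documents do not support that, because the very next sentence and the protocol take the median from Kaplan-Meier. Nor can one infer that the descriptive figures will be far too short: that needs an event share and an observation time that the documents do not give.

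What does not stand is that the second sentence cancels the first. It covers the median only and leaves the mean and SD with no valid method. The two sentences are separate instructions. In 8.4.2.1 Kaplan-Meier is named as the method of the worst-grade onset summary itself, which 8.3.3 does not do.

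**Conclusion.** The point holds in a limited form. The TTNM analysis contains a valid Kaplan-Meier median, and beside it a descriptive mean, SD and plain median that, under the SAP's own definitions, cover only patients with a new metastasis. The mean and plain median are biased short, and the plain median can contradict the Kaplan-Meier one.

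The direction follows from the definitions whenever some patients are censored before an event. The size is conditional: it is roughly the true value times the event share under exponential times and exponential censoring, with a simulated shortfall of about 8% to 83% across the two censoring patterns and event shares of 30% to 90%. The documents do not allow a choice within that range.

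A reader might also infer that the biased figure could mislead a decision about the drug. The plan does not support that either: Phase II is single-arm, unpowered and without a formal test, and no rule uses TTNM. The consequence is confined to the reported secondary result. It is still worth correcting, because the error is avoidable at almost no cost.

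**What to change.** - In SAP 8.3.3, delete the last three words of the first sentence, which order the descriptive summary. Report TTNM by Kaplan-Meier, with the number and percentage of patients who developed a new metastasis.
- In SAP 7.9.3, let the formula use the event date or the censoring date, and state that time-to-event variables are excluded from the continuous summary in SAP 8.
- Define the TTNM censoring date, for example the last evaluable tumor assessment, in line with the PFS rules in 8.2.2. Say also how death without a new metastasis and the start of new anticancer therapy are handled. Without such a rule the Kaplan-Meier analysis cannot be reproduced either, so deleting the three words is not enough.

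The cost is one clause removed and a few sentences added before database lock. There is less output to produce and no new data to collect.

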2 STUDY OBJECTIVES

Phase Ib

The **primary objectives** of this study are:

- To determine the safety, tolerability and maximum tolerate dose (MTD) of leronlimab (PRO 140) when combined with carboplatin in patients with CCR5+ mTNBC, to define a recommended Phase II dose of the combination.

The **secondary objective** of this study is:

- To determine the recommended Phase II dose for the combination of leronlimab (PRO 140) and carboplatin in patients with CCR5+ mTNBC.

Phase II

The **primary objective** of this study is:

- To evaluate the impact on progression-free survival (PFS) of the combination leronlimab (PRO 140) and carboplatin in patients with CCR5+ mTNBC.

[figure not shown]
The **secondary objectives** of this study are:

- To assess the overall response rate (ORR) and clinical benefit rate (CBR) of carboplatin – leronlimab (PRO 140) in patients with CCR5+ mTNBC;
- To assess benefit, based on time to new metastasis (TTNM);
- To assess the change in circulating tumor cells (CTCs) number after treatment; and
- To assess the safety and tolerability of the combination of leronlimab (PRO 140) and carboplatin in subjects with CCR5+ mTNBC.

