4.4 FOLLOW-UP PERIOD

Duration of Follow Up

- An End of Treatment (EOT) visit will be conducted 30 (\pm 3) days after the last treatment visit (i.e., after last dose of leronlimab (PRO 140) and carboplatin).
- All patients will be followed for adverse events for 30 days after last dose of leronlimab (PRO 140) and Carboplatin, or until the patient starts a new treatment, whichever occurs first.
- Subjects who discontinue treatment for unacceptable adverse event(s) will be followed until resolution or stabilization of the adverse event (i.e. the grade is not changing).
- If a subject stops treatment due to unacceptable adverse event(s) but has not demonstrated disease progression, then the subject will be followed with imaging studies every 9 weeks until the time of progression radiographically according to RECIST v1.1 criteria. In the event that a radiographic response is detected, then this event will be included as a response in the final analysis, and the time of progression used in calculation of the survival analysis.
- Subjects will be followed up by clinic visits or phone call or another method of contact, for survival status every 3 months (\pm 1 month) for 2 years after treatment discontinuation or until death, whichever occurs first.

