7.15.4. Evaluation of target lesions

- Measure LD (axial plane) for each target lesion
- Measure short axis for target lymph nodes
- Add these measurements to get the SLD
- If too small to measure, a default value of 5 mm is assigned. If the lesion disappears completely, the measurement is recorded as 0 mm.
- Splitting or coalescent lesions
 - If a target lesion fragments into multiple smaller lesions, the LDs of all fragmented portions are added to the sum
 - If target lesions coalesce, the LD of the resulting coalescent lesion is added to the sum

Table 7-3: Target Lesion Evaluation

Response	Definition
Complete Response (CR)	Disappearance of all target lesions. Any pathological lymph nodes (whether target or non-target) must have reduction in short axis to <10 mm.
Partial Response (PR)	At least a 30% decrease in the sum of diameters of target lesions, taking as reference the baseline sum diameters.
Progressive Disease (PD)	At least a 20% increase in the sum of diameters of target lesions, taking as reference the smallest sum on study (this includes the baseline sum if that is the smallest on study). In addition to the relative increase of 20%, the sum must also demonstrate an absolute increase of at least 5 mm. (Note: the appearance of one or more new lesions is also considered progression).

Response	Definition
Stable Disease (SD)	Neither sufficient shrinkage to qualify for PR nor sufficient increase to qualify for PD, taking as reference the smallest sum diameters while on study.

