- (3) Treatment Period: Subjects who meet the eligibility criteria will have completed following evaluations and assessments before receiving treatment: a) review of medical and medication history; b) physical examination, vital signs and documentation of ECOG performance status; c) ECG; d) routine serum biochemical, hematologic, urine pregnancy (if applicable) and urine laboratory assessments. Additionally, a blood sample will be collected prior to treatment administration for CTCs PD-L1/CCR5, and CTC CAMLs analysis.

Each treatment cycle will consist of 21 days. Leronlimab (PRO 140) will be administered subcutaneously weekly on Days 1, 8, and 15 in combination with carboplatin AUC 5 on Day 1 of each cycle (every 21 days). Day 1 of Cycle 2 begins at Day 22. The study treatment will be administered by a licensed medical professional at clinic site or self-administered by subjects at home.

Subjects will be allowed to continue treatment under subsequent treatment cycles until any one of the following occurs: progressive disease or unacceptable toxicity or withdrawal of consent.

(4) Follow-Up Period: An End of Treatment (EOT) visit will be conducted 30 (\pm 3) days after the last treatment visit (i.e., after last dose of leronlimab (PRO 140) and carboplatin). Additionally, follow-up will be done for survival status, by clinic visits or phone or another method of contact, every 3 months (\pm 1 month) for 2 years after treatment discontinuation or until death, whichever occurs first.

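### The Kaplan-Meier median for time to new metastasis has no rule for other progression or death, and it cannot be read as benefit

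*SAP*

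**What the plan says.** - **Analysis.** SAP 8.3.3 states that "Kaplan-Meier analysis will be used to depict the median time (days) to new metastases", with times computed by the formula in SAP 7.9.3, which counts from first treatment.
- **Event.** Protocol 8.7.3.1 defines it as "Recorded time from baseline metastatic disease (at time of enrollment) to the time of development of new metastasis in different site". New lesions in a site already involved are recorded but fall outside this definition.
- **Objective.** Protocol section 2 lists, among the Phase II secondary objectives, "To assess benefit, based on time to new metastasis (TTNM"). SAP 2.3 repeats it.
- **Link to progression.** Protocol 7.15.4 (Table 7-3) notes that "the appearance of one or more new lesions is also considered progression".
- **Imaging.** Scans are tied to treatment cycles, and SAP 2.1 continues treatment "until any one of the following occurs: progressive disease or unacceptable toxicity or withdrawal of consent". Under Protocol 4.4, when a patient stops for an adverse event without progression, "the subject will be followed with imaging studies every 9 weeks until the time of progression"; Protocol 4.4.2 carries the same limit. Other patients off treatment are followed for survival.
- **Later observation.** There are two routes: an end-of-treatment scan (Protocol 7.15 and Table 4-1 footnote 8, although the visit list in 4.4.1 omits it), and treatment beyond progression after an initial disease flare (Protocol 7.15.6).
- **Censoring.** SAP 8.2.2 sets out detailed censoring rules for PFS. SAP 8.3.3 has none for TTNM, and SAP 7.4 rules out sensitivity analyses.

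**The concern.** Three kinds of first event are not TTNM events: growth of known lesions, a new lesion in a site already involved, and death. SAP 8.3.3 does not say what happens to these patients. A Kaplan-Meier analysis has only events and censored times, so they can enter only as censored, on a date the plan leaves open. Censoring at that point assumes that a patient who has just progressed, or has died, carries the same later risk of new-site metastasis as a patient still under control. For death the assumption has no meaning. For progression it can hardly be checked, because regular scans have ended.

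The event definitions are also nested: a new-site metastasis is itself a progression. A TTNM curve on or above the PFS curve is therefore expected whether or not the drug affects metastasis. The trial has one arm and the documents give no TTNM reference value, so a long median filed under an objective worded as benefit could be given a meaning it does not have.

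**Working it through.** The documents state no TTNM figure, so there is nothing to reproduce.

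**Inputs.** Median PFS of about 5 months (SAP 2.1) and 30 Phase II patients (SAP section 3). Assumed, because the documents do not give them: constant hazards, and a share f of first PFS events that are new-site metastases.

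**Step 1: ordering.** Suppose patients leave the risk set on the same dates for TTNM and PFS. At each event time the number at risk n is the same, and the TTNM events d cannot outnumber the PFS events. Every factor 1 − d/n is then at least as large for TTNM, so its curve lies on or above the PFS curve.

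**Step 2: size.** The total hazard is λ = ln 2 / 5 per month, and the new-site hazard is fλ.

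- Kaplan-Meier median, other first events censored: ln 2 / (fλ) = 5/f
- One minus Kaplan-Meier at 12 months: 1 − exp(−12fλ)
- First-event cumulative incidence at 12 months: f × (1 − exp(−12λ)) = f × 0.8105

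| f (assumed) | KM median, months | 1 − KM, 12 months | Cumulative incidence, 12 months |
|---|---|---|---|
| 0.4 | 12.5 | 49% | 32% |
| 0.5 | 10.0 | 57% | 41% |
| 0.6 | 8.3 | 63% | 49% |

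The cumulative incidence tends to f. It therefore never reaches 50% at f = 0.4 or 0.5, although Kaplan-Meier reports a median for both. At f = 0.6 it reaches 50% at 5 × log2(6) = 12.9 months, against 8.3 from Kaplan-Meier.

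**Step 3: trials of 30.** Simulation used 4,000 trials, scans at weeks 6, 12 and 18 and then every 9 weeks, 10% of first events as deaths (assumed) and a 24-month cut-off. Here f is the share among non-death events. A median not reached counts as above.

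| f | TTNM median above PFS median | Equal | TTNM median not reached |
|---|---|---|---|
| 0.3 | 100% | 0% | 45% |
| 0.5 | 99% | 1% | 6% |
| 0.7 | 92% | 8% | 0% |
| 0.9 | 64% | 36% | 0% |
| 1.0 | 41% | 59% | 0% |

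The TTNM median was never below. Adding an end-of-treatment scan 3.5 weeks after progression left the first figure at 99% for f = 0.5. If PFS is censored at toxicity discontinuation (assumed rate 0.03 per month) while TTNM is still followed, TTNM fell below PFS in 0% of trials up to f = 0.7, 1% at f = 0.9 and 3.5% at f = 1.0.

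**Step 4: what the missing scans hide.** Let the new-site hazard after another progression be r times the hazard before it. Ignoring death and scanning throughout, the proportion free of new-site metastasis is

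S(t) = exp(−λt) + (1 − f)λ × [exp(−gt) − exp(−λt)] / (λ − g), with g = rfλ (taken as a limit when g = λ).

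At f = 0.5 the median is 12.1, 10.0, 8.3 or 7.4 months for r = 0.5, 1, 2 or 3. Kaplan-Meier with censoring at progression gives 10.0 in every case.

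**The case against.** The strongest reply is that this is a descriptive secondary endpoint in 30 patients. SAP section 5 calls the study hypothesis generating and plans no formal test. The documents plan no comparison of TTNM with PFS. Protocol 1.5 lists PFS, response rate and circulating tumor cells as its hypotheses, with reduced metastasis only as a mechanism for PFS. The shares f are assumed; at f = 0.9 the medians differ by only 0.6 months (5.6 against 5.0). All of this stands and limits the weight of the point. It does not supply the missing rule.

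A reader might infer more than the documents support:

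- **That new metastases cannot be seen after first progression.** The end-of-treatment scan and treatment beyond progression for flare allow some observation. It is not regular.
- **That the TTNM median must exceed median PFS.** The medians can tie, or the TTNM median may not be reached. Nor are TTNM events strictly a subset of PFS events: SAP 8.2.2 censors PFS at toxicity discontinuation, while Protocol 4.4 keeps imaging those patients.
- **That stopping scans causes the ordering.** The nested definitions cause it. In Step 4, stopping scans lengthens the median only if r is above 1.
- **That Kaplan-Meier flatters the drug throughout.** One minus Kaplan-Meier overstates the incidence of new metastasis, which counts against the drug.

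**Conclusion.** The point holds as a specification gap with a cheap remedy. The planned median rests on an unstated treatment of competing events and on an independence assumption that the imaging schedule can barely test. With shared censoring it will be at least as long as median PFS, and usually longer, without any drug effect. For f between 0.4 and 0.6 it would be 8.3 to 12.5 months against a PFS of 5, and one minus Kaplan-Meier would overstate 12-month first-event incidence by about 14 to 16 percentage points (63 − 49 and 57 − 41).

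These sizes depend on constant hazards and the assumed shares. The missing rule and the nested definitions do not. The documents do not show that anyone intends to present the TTNM–PFS gap as an effect; the risk lies in how a median under this objective could be read.

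**What to change.** In Protocol 8.7.3.1 and SAP 8.3.3:

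1. Make the main TTNM summary the cumulative incidence of new-site metastasis as first event. Treat progression without a new site and death as competing events, and give 95% confidence intervals at 6 and 12 months from first dose.
2. State the censoring rules for new anticancer therapy and for missed scans.
3. Tabulate the pattern of first progression: new site, new lesion in the same site, existing lesions only, death.
4. List later new metastases from end-of-treatment or post-progression scans separately, so that they are not lost.
5. Do not present a TTNM median beside median PFS as evidence of benefit.

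The cost is wording in two documents and one standard analysis of RECIST data already collected, with no added scans. Protocol 8.7 has the SAP approved before database lock. The downside is that a median may not be reportable. Precision will also be modest: at 41% with 30 patients and no censoring, the half-width is about 1.96 × √(0.405 × 0.595 / 30) = 18 percentage points.
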